9.2. Statistical Methodology

A summary of the data will be prepared for all measurement time points. Summaries of the changes observed between the pre-operative (baseline) and the 3 month post-operative visits will also be summarized. Comparison of the laser and manual groups in terms of post-operative corneal astigmatism, uncorrected visual acuity and residual refractive cylinder and spherical equivalent refraction will be documented.

For variables measured on a continuous scale, these summaries will include the sample size, as well as the mean, standard deviation, median, minimum, and maximum. These summaries will be provided for all eyes completing the study.

9.2.1. Within-treatment Changes

For variables measured on a continuous scale, the statistical significance of within-treatment changes between time points will be investigated using paired t-tests. For variables measured on an ordinal categorical scale, the Wilcoxon signed-rank test will be employed.

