5. OBJECTIVE(S)

The objective of this study is to compare the effectiveness of LenSx laser arcuate relaxing incisions vs. manual (blade) arcuate relaxing incisions in patients with low, but significant, levels of astigmatism.

The primary outcome measure will be the residual refractive astigmatism. Secondary outcome measures will be the percentage of eyes with refractive astigmatism ≤ 0.50 D, uncorrected monocular distance visual acuity, corneal astigmatism and manifest refraction at 3 months. Exploratory endpoint will be the topographic changes.

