10. SAMPLE SIZE JUSTIFICATION

The sample size [based on a power of 0.8, an alpha of 0.05, an estimated standard deviation of postoperative refractive astigmatism of 0.4D (from the literature) and an expected improvement on average of 0.25D with laser incisions] would be 41 subjects.

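### Section 9 names no between-eye test or confidence interval for the laser-manual difference in the primary endpoint; the only tests it names are for change over time within each treatment.

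*Combined protocol and SAP*

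**What the plan says.** Section 5 sets the objective, to "compare the effectiveness of LenSx laser arcuate relaxing incisions vs. manual (blade) arcuate relaxing incisions", and the endpoint: "The primary outcome measure will be the residual refractive astigmatism". Section 8.1.2 randomizes within the subject, one eye to laser and the fellow eye to the blade. Section 10 arrives at 41 subjects from power 0.8, alpha 0.05, a standard deviation of 0.4 D for postoperative refractive astigmatism, and "an expected improvement on average of 0.25D with laser incisions".

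Section 9.2 does commit to comparing the laser and manual groups. It lists corneal astigmatism and uncorrected acuity, and ends: "residual refractive cylinder and spherical equivalent refraction will be documented". For continuous variables, "these summaries will include the sample size, as well as the mean, standard deviation, median, minimum, and maximum". Change from baseline is also to be summarized.

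The only named tests are in 9.2.1, under a heading limited to within-treatment changes: "the statistical significance of within-treatment changes between time points will be investigated using paired t-tests". The Wilcoxon signed-rank test is named there for ordinal variables. Section 9.3 sets alpha at 0.05 for any test performed, without naming one or stating sidedness. Section 9 has no subsection on between-treatment analysis and mentions no confidence interval.

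**The concern.** The trial's question is a difference between fellow eyes. A test of change from baseline within the laser eyes, and another within the manual eyes, shows whether astigmatism changed after each technique. Neither shows whether the techniques differ, since both arms can improve significantly whether or not laser is better.

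If Section 9 is followed literally, the report will hold two sets of group summaries and some within-arm p-values, but no pre-specified test or interval for the contrast that the trial was sized to detect.

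The text also leaves open whether the eyes are to be analysed as pairs. The design is paired. However, Section 9.2 speaks of groups, Section 9.1 defines the efficacy set by eye, and the standard deviation in Section 10 is that of the outcome, not of the between-eye difference. Section 2 states that there is no masking, so the method could be chosen by people who have already seen the results.

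**Working it through.** **Inputs.** From Section 10: 41 subjects, SD 0.4 D (read as per eye), difference 0.25 D, alpha 0.05, power 0.8. From Section 8.1.2: one laser eye and one manual eye per subject, so 41 pairs. Assumed: between-eye correlation ρ of -0.2, 0, 0.25 and 0.5, because the documents give none, and normally distributed data.

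**Step 1: reproduce 41.** For two independent groups, two-sided:

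n = 2 × [(1.960 + 0.842) × 0.4 / 0.25]² = 40.2, so 41 per group.

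One-sided alpha gives about 32. Two-sided testing is therefore inferred from the figure; neither Section 9.3 nor Section 10 states it. The paired normal formula multiplies this n by (1 − ρ), so at ρ = 0 it also gives 40.2.

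**Step 2: paired t-test with 41 pairs.** SD of the difference = 0.4 × √[2(1 − ρ)]. Power comes from the noncentral t distribution with 40 degrees of freedom. The 95% CI half-width = 2.021 × SD of difference / √41.

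**Step 3: unpaired t-test on the same eyes.** This has 80 degrees of freedom. Power and type I error come from simulation of 200,000 trials per setting. The half-width is about 1.990 × 0.4 × √(2/41) = 0.176 D at every ρ.

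| ρ (assumed) | SD of difference (D) | Paired power | Paired half-width (D) | Unpaired power | Unpaired type I error |
|---|---|---|---|---|---|
| -0.2 | 0.620 | 71% | 0.20 | 78% | 7% |
| 0 | 0.566 | 79% | 0.18 | 80% | 5% |
| 0.25 | 0.490 | 89% | 0.15 | 83% | 2.4% |
| 0.5 | 0.400 | 97% | 0.13 | 88% | 0.7% |

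The paired test has 5% type I error in every row. At ρ = 0 its power with 41 pairs is 78.9%, and 43 pairs are needed for 80%, because the t distribution asks slightly more than the normal formula.

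**Step 4: skewness.** Cylinder magnitude cannot be negative. With gamma-distributed data (SD 0.4 D; assumed means 0.5 D in both arms under the null, and 0.4 v 0.65 D or 0.5 v 0.75 D under the alternative), the paired t-test's type I error was 4.8% to 5.0% over latent correlations of 0, 0.25 and 0.5. Power was 78% to 79%, 87%, and 95% to 96%. The paired t-test is therefore a reasonable primary choice at this sample size.

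**The case against.** The strongest reply is that the plan settles most of the analysis. Section 9.2 promises the comparison, Section 9.3 fixes alpha, and Section 10 fixes the contrast, the effect and the power, so a competent analyst would supply a paired t-test. Even the wrong choice does limited harm: at zero correlation it is worth about one point of power, and at positive correlation the unpaired test is conservative and still exceeds the planned 80%. Inflated false positives appear only at ρ = -0.2, a value with no support in the documents.

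Those figures stand, and they limit the numerical cost. They do not supply the missing method, and they do not measure the freedom to choose it after seeing the data. Nor is pairing clearly implied, given the group wording, the eye-level efficacy set and a sample size that the independent-groups formula reproduces. The paired t-test is also not the only valid choice: a mixed model or a primary signed-rank test would respect the pairing too.

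A reader might infer four stronger things that the documents do not support:

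- **That no laser-manual comparison is planned.** Section 9.2 plans one; it lacks a test and an interval.
- **That the within-arm tests will decide the laser-manual question.** Section 9.2.1 does not say so. The risk is that they are the only pre-specified p-values and could be misread.
- **That the method will be chosen after the data are seen.** The documents do not say when it will be chosen; they only leave this possible.
- **That the primary endpoint is already fixed at 3 months.** The 3-month wording in Section 9.2 belongs to the summaries of change from baseline, not to the comparison sentence, and refraction is also measured at 1 month.

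**Conclusion.** The point holds and should be fixed before analysis, because it concerns the primary endpoint and the plan as written gives no inference on it. The defect is an omission in Section 9.2. The sentence in 9.2.1 is sound for its own purpose but answers a different question.

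The size depends on the between-eye correlation, which is unknown. At zero the choice of method is nearly neutral. At an assumed 0.5 the unpaired analysis gives up about 9 points of power (97% v 88%), and its half-width is about 0.18 D where the paired one is 0.13 D. At an assumed -0.2 the unpaired test exceeds its stated error rate. Of the two t-tests, only the paired one holds 5% across the range. These figures assume 41 complete pairs, a per-eye SD of 0.4 D and two-sided testing.

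It would be wrong to conclude that the sample size is in error. The figure of 41 reproduces, and 41 pairs give about 79% power at zero correlation and more if fellow eyes are positively correlated.

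**What to change.** In Section 9.2, name the primary analysis: for each subject, residual refractive cylinder in the laser eye minus that in the manual eye at one stated visit, with a two-sided paired t-test at alpha 0.05, the mean difference and its 95% CI. Add a signed-rank test on the same differences as a sensitivity analysis. The sponsor should confirm the visit. Three months is the natural candidate, since it is the final visit and Section 2 labels corneal astigmatism and manifest refraction as 3-month endpoints.

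State that the tests in 9.2.1 are supportive and not the basis for the laser-manual conclusion.

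Three smaller edits belong in the same revision:

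- Apply paired methods to the other between-eye comparisons and label them as secondary.
- Add the proportion of eyes at or below 0.50 D. Section 5 makes it a secondary endpoint ("Secondary outcome measures will be the percentage of eyes with refractive astigmatism" at that threshold), but the comparison list in 9.2 omits it. McNemar's test with the paired difference and its 95% CI would serve.
- Reconcile Sections 6.4, 8.1.2 and 9.1. When surgery is not completed, 6.4 requires the subject's data to be excluded from efficacy and 8.1.2 only permits it, while 9.1 defines the efficacy set by eye. State whether an eye or a subject leaves the set, and how a subject with one evaluable eye is handled.

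The cost is a few lines of text, with no new data, visits or patients. The small downside is that a pairs-only analysis drops subjects with one evaluable eye.

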6.2. Inclusion Criteria

Subjects are eligible for the study if they meet the following criteria:

Note: Ocular criteria must be met in both eyes.

- are willing and able to understand and sign an informed consent;
- are willing and able to attend all study visits;
- are more than 40 years of age, of either gender and any race;
- are presenting for cataract surgery or refractive lens exchange with a desire to reduce astigmatism and will be implanted with a non-toric lens

- have good ocular health, with no pathology that compromises visual acuity (outside of residual refractive error and cataract)
- have 0.50D to 1.75D of regular corneal astigmatism
- have potential acuity of 20/25 or better
- Are scheduled to have a non-toric monofocal IOL (SN60WF) lens implanted in both eyes

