8.1.2. Operative (Surgery)

All subjects will receive a Betadine prep in the usual sterile fashion. They will then be taken to the operative room and treated with the assigned method. Each patient would undergo a randomized process of one eye obtaining LenSx laser arcuate(s) and the contralateral eye obtaining manual blade arcuate(s). Accepted nomograms would be utilized to calculate the exact length and positioning of the arcuate incisions.

Outside of the femtosecond laser arcuate incisions, no other femtosecond procedure will be performed on any eyes. The corneal surgical incisions, capsulorhexis and fragmentation will be performed without use of the femtosecond laser system.

All eyes will be implanted with a non-toric monofocal IOL, specifically the SN60WF lens (Alcon, Fort Worth, TX).

Surgical findings will be recorded and any adverse events/serious adverse events (AEs/ SAEs) occurring during surgery will be noted at this visit. Any other problems during surgery and comments regarding surgery will be documented.

Any subject whose surgery is not completed successfully will be documented in the appropriate case report form. These subjects will be monitored for safety but clinical performance data may be excluded from the analysis.

Immediately following the laser treatment, the arcuate incisions will be opened at an operating microscope. All study subjects will be placed on an appropriate antibiotic and steroid drop QID for one week.

For the following three weeks, only the steroid drop will be continued on a tapered dose.

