8.2.1. Manifest Refraction

Perform a manifest refraction with a high contrast logMAR chart under photopic lighting conditions (>85 cd/m²). Document refraction results with sphere, cylinder and axis readings. If uncorrected visual acuity is not improved by manifest refraction, use zero for sphere and cylinder and draw a line through the blank for the axis.

Note: Each subject should be manually refracted to his/her best correction by an ophthalmologist, optometrist, or a skilled technician using a phoropter or trial lenses.

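### The only tests the plan names are within-arm changes over time; for refractive cylinder and acuity these mix lens replacement with the incision, while the laser-versus-manual comparison has no named test

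*Combined protocol and SAP*

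**What the plan says.** Section 9.2.1 (Within-treatment Changes) states that "the statistical significance of within-treatment changes between time points will be investigated using paired t-tests" for continuous variables, and assigns the Wilcoxon signed-rank test to ordinal ones. It lists no variables and no pair of visits. Section 9.3 sets alpha at 0.05 for any test. No other test is named in the plan.

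Section 9.2 points to the interval of interest: "Summaries of the changes observed between the pre-operative (baseline) and the 3 month post-operative visits will also be summarized". Table 14-1 schedules manifest refraction and uncorrected and corrected distance acuity before surgery and again at 1 and 3 months.

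For the two techniques, section 9.2 offers a "Comparison of the laser and manual groups in terms of post-operative corneal astigmatism, uncorrected visual acuity and residual refractive cylinder and spherical equivalent refraction", but says only that it is to be documented.

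On the surgery, section 6.2 admits patients who "are presenting for cataract surgery or refractive lens exchange with a desire to reduce astigmatism", and section 8.1.2 adds: "All eyes will be implanted with a non-toric monofocal IOL". One eye of each patient receives laser arcuate incisions and the other receives blade incisions. Section 8.1.2 also shows that other corneal incisions are made in every eye: "The corneal surgical incisions, capsulorhexis and fragmentation will be performed without use of the femtosecond laser system".

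Section 8.2.1 asks staff to "Document refraction results with sphere, cylinder and axis readings", but section 9 has no analysis that uses axis.

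**The concern.** Pre-operative refractive cylinder reflects the cornea and the natural lens together. At 3 months the natural lens has gone and a non-toric implant is in place, so the cylinder is essentially corneal. The change between the two therefore contains the loss of the lens's own cylinder as well as the incision effect. Acuity has the same problem, because removing a cataract can improve it without any incision. No study eye has lens surgery alone, so the within-arm data cannot separate the two sources.

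At stake is what the p-values would mean. The objective in section 5 and the calculation in section 10 both concern laser versus manual. The plan attaches significance tests to contrasts that do not answer that question and attaches none to the one that does. A significant change in one arm and a non-significant change in the other would also not show that the techniques differ.

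**Working it through.** **1. The plan's own figure.** Section 10 gives power 0.80, alpha 0.05, SD 0.4 D and a difference of 0.25 D. With a two-sided test (sidedness is not stated), n = 2 × [0.4 × (1.960 + 0.842) / 0.25]² = 40.19, rounded up to 41. Power at 41 is 0.808. The stated 41 reproduces. It is built on the laser-versus-manual difference, not on change over time.

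**2. Do refractive cylinder and acuity fall under section 9.2.1?** The section covers all continuous variables between time points. Table 14-1 has refraction and acuity measured before and after surgery, and section 9.2 singles out the baseline-to-3-month change. So they do, but by this combination and not by name. The same wording also covers corneal astigmatism, and 1-month-to-3-month change, where loss of the lens plays no part.

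**3. Acuity with zero incision effect (assumed inputs).** For a paired t-test with n = 41, the non-centrality is (gain / SD of change) × √41, with √41 = 6.403. Suppose lens surgery alone gains 0.10 logMAR:

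| SD of change | Non-centrality | Probability of p < 0.05 |
|---|---|---|
| 0.15 | 4.27 | 0.99 |
| 0.20 | 3.20 | 0.88 |
| 0.30 | 2.13 | 0.55 |

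**4. Refractive cylinder with zero incision effect (simulation, 4,000 trials of 41 eyes).** On the double-angle plot, pre = |C + L + noise| and post = |C + noise|; the paired t-test is on post minus pre.
- From section 6.2: corneal cylinder C between 0.50 and 1.75 D, taken as uniform.
- Assumed: mean lenticular cylinder L as in the table, with SD 40% of that mean; measurement noise 0.25 D; meridian scatter of 0.5 radian on the doubled angle (28.6° / 2, about 14°).

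| Assumed lenticular cylinder (mean) | Corneas against-the-rule | Mean change (D) | Rejects |
|---|---|---|---|
| none | 50% | 0.00 | 5% |
| 0.25 D, random axis | 50% | −0.018 | 7% |
| 0.50 D, random axis | 50% | −0.079 | 21% |
| 0.75 D, random axis | 50% | −0.180 | 51% |
| 0.50 D, against-the-rule | 50% | −0.060 | 11% |
| 0.50 D, against-the-rule | 20% | +0.155 | 61%, as an increase |
| 0.50 D, against-the-rule | 80% | −0.275 | 97%, as a reduction |

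In the same runs, the test on change in corneal astigmatism rejected in 4.4% to 5.4% of trials. Those runs gave the main corneal incisions no effect, so this shows only that the lens does not contaminate the corneal measure.

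**5. The randomized contrast.** A paired between-eye test of post-operative cylinder, with no true difference and 41 pairs, rejected in 4.4% of simulated trials. For power, the SD of the between-eye difference is 0.4 × √[2(1 − ρ)]. At assumed inter-eye correlations ρ of 0, 0.25 and 0.50 it is 0.566, 0.490 and 0.400 D, and a paired t-test with 41 pairs has power 0.79, 0.89 and 0.97 for 0.25 D.

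**6. Axis.** A 1.00 D corneal cylinder that ends at 0.50 D on the same axis, or at 0.50 D on the opposite axis, changes by 0.50 D in magnitude both times. The vector changes are 1.00 − 0.50 = 0.50 D and 1.00 + 0.50 = 1.50 D. A 1.00 D effect placed 30° off axis leaves 2 × 1.00 × sin 30° = 1.00 D, a magnitude change of zero.

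**The case against.** The strongest reply is that section 9.2.1 only asks whether values changed between visits, and a paired t-test answers that validly. This stands. A reader might infer that the sponsor intends to present within-arm p-values as proof that the incisions work. No section says so: the objective, the sample size and the listed comparisons all concern laser versus manual.

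A reader might also infer that lens removal biases the trial's main comparison or undermines the 41 subjects. It does neither. Both eyes of every patient have the lens replaced, and the primary outcome is residual cylinder after surgery, not change from baseline.

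A third tempting reading is that ignoring axis is an error throughout. For the primary endpoint it is not: 0.50 D left undercorrected and 0.50 D flipped are the same residual magnitude, which is what the endpoint measures. Axis matters only where a change in astigmatism is meant to describe what the surgery did. Section 9 does not say how change would be derived, so subtraction of magnitudes is a default reading and not a stated rule.

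Finally, one might size the problem from a single eye whose corneal and lenticular cylinders align exactly, and set that against the 0.25 D in section 10. That compares a one-eye extreme with a difference between arm means; across a group, aligned and opposed eyes partly offset.

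What survives is narrower: the tested contrasts do not isolate the incision, and the contrast that answers the objective is left without a test.

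**Conclusion.** The concern holds as a moderate weakness of analysis and interpretation. As worded, the named tests reach pre-to-3-month change in refractive cylinder and acuity, and for these variables a significant within-arm result does not isolate the incision effect. This follows from the design alone: lens replacement in every eye and no eye with lens surgery only.

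Any numerical size is an assumption, because the documents give no lenticular cylinder and no acuity gain from lens surgery. With zero incision effect and 41 eyes, the cylinder test rejects from about 5% to over 90% of the time, and in either direction, depending on the assumed lens. The acuity test rejects in 55% to 99% for an assumed gain of 0.10 logMAR. The randomized laser-versus-manual contrast and the 41 subjects are unaffected. The point matters mainly because that contrast has no named test.

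**What to change.** 1. In section 9.2, name the primary analysis: a paired test of the within-subject, between-eye difference in residual refractive cylinder magnitude at 3 months, with its confidence interval. The primary outcome measure stays as it is.
2. In section 9.2.1, label pre-to-post changes in refraction and acuity as descriptive and report them without p-values.
3. Where pre-to-3-month corneal astigmatism is tested, compute the vector change from magnitude and axis. Express it as signed components relative to each eye's pre-operative steep meridian; in fixed coordinates, flattening at 90° in some eyes and at 180° in others would cancel. Prespecify one of the devices listed in section 8.2.3. Describe the result as total surgical corneal change, because the main corneal incisions also contribute, and use the between-eye difference in that component as the incision comparison.

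The cost is a few within-arm p-values and a short derivation. No visit, measurement or subject is added: refractive axis is already recorded, and corneal astigmatism is already measured before surgery and at 1 and 3 months. One item to check is that the case report form captures corneal axis as well as magnitude, since section 8.2.3 does not say so.

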9.3. General Statistical Considerations

The statistical analyses will be performed using Statistica, version 12 or higher. Any statistical tests of hypotheses will employ a level of significance of alpha=0.05.

10. SAMPLE SIZE JUSTIFICATION

The sample size [based on a power of 0.8, an alpha of 0.05, an estimated standard deviation of postoperative refractive astigmatism of 0.4D (from the literature) and an expected improvement on average of 0.25D with laser incisions] would be 41 subjects.

